4.2 Randomised treatment period

4.2.1 Randomisation and treatment period

The inclusion/exclusion criteria at the randomisation visit (Visit 4) will be confirmed. Before randomisation the subject's compliance with his/her maintenance medications and ePRO completion must be confirmed.

Subjects confirmed to be eligible will be randomised at Visit 4 in a 1:1:1:1 ratio to receive benralizumab 10 mg, 30 mg or 100 mg or placebo every 4 weeks for the first 3 doses and then every 8 weeks thereafter with the last dose of IP administered at week 48 and last treatment evaluation performed at week 56.

The first dose of the IP will be administered at Visit 4 after the subject's randomisation via the IWRS/IVRS.

Following randomisation, the subject will enter the 56-week double-blind treatment period with the last dose of benralizumab/placebo administered at Visit 17 (week 48).

Subjects will have scheduled clinic visits at 4-week intervals up to Visit 7 and then at 8 week intervals up to Visit 19 to complete protocol-specific assessments and IP administration, as

listed in Table 3. Telephone visits will also occur as per the study plan, listed in Table 3. The restrictions noted in section 3.5 will continue to apply throughout the treatment period. In case of a COPD worsening/exacerbation (see section 5.1.1), subjects should be evaluated at the study centre, when feasible, at an unscheduled visit, or a scheduled visit if the worsening happens to fall within a scheduled visit window.

Subjects will continue to record their COPD symptoms and responses to the questionnaires using the ePRO device throughout the 56-week treatment period (see section 5.1.3 for details).

At week 56 subjects will come to the centre for the End of Treatment (EOT) visit.

Subjects who prematurely discontinue from IP (see section 3.6) should return to the study centre and complete procedures described for the EOT visit 12 weeks (± 7 days) after the last dose of IP.

Subjects will return the ePRO device and all background/rescue medications at the EOT visit.

Subjects will return the ePRO device at week 56.

Subjects who prematurely discontinue from IP should follow the procedures and visit schedule described in section 3.6.

Completion, or early termination of the treatment will be registered via IWRS/IVRS for each subject.

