8.2 Sample size estimate

The study will recruit subjects with blood eosinophil counts $<220/\mu\text{L}$, $220\text{-}299/\mu\text{L}$, and $\geq 300/\mu\text{L}$. The approximately 2:1 ratio between $\geq 220/\mu\text{L}$ and $<220/\mu\text{L}$ allows analysis of the primary population for subjects most likely to respond to benralizumab (i.e. $\geq 220/\mu\text{L}$), while still including subjects below this threshold in order to help understand efficacy and safety in this group. The study is powered for the exacerbation rate comparisons of the subjects with blood eosinophils $\geq 220/\mu\text{L}$ (primary efficacy analysis).

For the primary endpoint annual COPD exacerbation rate, 348 subjects with baseline blood eosinophil counts $\geq 220/\mu\text{L}$ per treatment arm (1392 total) will need to be randomised to achieve 90% power of detecting a 30% reduction in both the 30mg and 100mg benralizumab dose groups versus placebo based on a Hochberg Procedure (Hochberg 1988). This calculation has assumed two-sided 4% alpha level tests, an annual placebo rate of 0.93 events/subject (1.0 events/subject/56 weeks), a negative binomial shape parameter of 0.4, and a dropout rate of 10%. The sample size calculation is based on simulations and has accounted for the power loss from a proposed futility analysis (Section 8.5.6).

As stated previously an approximately 2:1 ratio will be used for subjects with blood eosinophil counts $\geq 220/\mu\text{L}$ and $<220/\mu\text{L}$. Therefore this study will randomise 174 subjects/arm (696 total) with baseline blood eosinophil counts $<220/\mu\text{L}$. An additional 20 subjects/arm will also be recruited to the 220-299/ μL cohort to better characterize patients within this cohort. This addition results in 368 subjects/arm in the $\geq 220/\mu\text{L}$ cohort (1472 total). A total of 2168 subjects are expected to be randomised in this study. Details of the estimated numbers of recruited subjects/arm in each cohort ($<220/\mu\text{L}$, $220\text{-}299/\mu\text{L}$, $\geq 300/\mu\text{L}$) are described in the SAP.

The sample size necessary to achieve a stated power (90% in our case) in this study is calculated based on the estimate of overall exacerbation rate and shape parameter from the negative binomial model (Section 8.5.1). In order to better estimate the overall exacerbation

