8.5 Methods for statistical analyses

The primary analysis of the primary and key secondary endpoints will include all data captured during the 56-week treatment period, regardless of whether study treatment was prematurely discontinued, or delayed, and/or irrespective of protocol adherence.

Demography and baseline characteristics will be summarized by treatment group for the full analysis set. In the event that there are major differences between the full analysis set and safety analysis set, these summaries will also be repeated for the safety analysis set.

Testing strategy to account for multiplicity considerations

To account for multiplicity to test the primary (exacerbation) and two key secondary endpoints (FEV₁ and SGRQ) for each of the 30mg and 100mg dose groups (for subjects with baseline blood eosinophils $\geq 220/\mu\text{L}$) a testing strategy will be followed to control the overall type I error rate at level 0.05. The testing strategy will be according to the following gate keeping procedure:

Step 1: Perform the two tests of annual COPD exacerbation rate (one test for each dose vs. placebo) at the family wise error rate (FWER) of 0.04 using a Hochberg Procedure ([Hochberg](#))

[figure not shown]
1988). If both p-values are less than 0.04, then proceed to Step 2; else if the smaller p-value is less than 0.02 then proceed to Step 2a; otherwise no null hypothesis is rejected

Step 2: Test the two key secondary endpoints for both doses as one family at the FWER of 0.05 using a Holm Procedure (Holm 1979).

Step 2a: Test the two secondary endpoints for the smaller-p-value dose at the FWER of 0.01 using a Holm Procedure.

The gatekeeping procedure is also shown in the diagram below:

Figure 4 Gatekeeping Procedure

Since the correlation of the two test statistics for COPD exacerbation rate in the Step 1 is positive, the FWER of the Hochberg Procedure is strongly controlled at 0.04. The overall FWER of the gatekeeping procedure is strongly controlled at 0.05.

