Change from baseline in pre-dose/pre-bronchodilator FEV_1 at Week 56 will be compared between each of the three benralizumab dose groups and placebo using a repeated measures analysis on subjects with a baseline pre-dose/pre-bronchodilator FEV_1 and at least one post-randomisation pre-dose/pre-bronchodilator FEV_1 in the full analysis set. The dependent variable will be the change from baseline in pre-bronchodilator FEV_1 at post-baseline protocol-specified visits (up to the EOT visit). Treatment group will be fitted as the explanatory variable, and eosinophil cohort ($220-299/\mu\text{L}$ or $\geq 300/\mu\text{L}$), country, background therapy (ICS/LABA, LABA/LAMA, or ICS/LABA/LAMA), visit, the interaction between visit and treatment and baseline pre-bronchodilator FEV_1 will be fitted as covariates. Visit will be fitted as a categorical variable, and the variance-covariance matrix will be assumed to be unstructured. If the procedure does not converge then a compound symmetric variance-covariance matrix will be used instead. The model is:

*Change in FEV₁ = Treatment group + eosinophil cohort (220-299/ μ L or \geq 300/ μ L) + baseline FEV₁ + country + background therapy (ICS/LABA, LABA/LAMA, or ICS/LABA/LAMA) + visit + treatment*visit*

Change from baseline in SGRQ total score and three domain scores (symptoms, activity, and impacts) at Week 56 will be analyzed separately using a similar model as the above model for change from baseline in pre-dose/pre-bronchodilator FEV₁.

Proportion of subjects with \geq 4-point decrease (improvement) in SGRQ total score at Week 56 in each of the three benralizumab dose groups will be compared with the proportion in the placebo group using a Cochran–Mantel–Haenszel test controlling for eosinophil cohort (220-299/ μ L or \geq 300/ μ L), country, and background therapy (ICS/LABA, LABA/LAMA, or ICS/LABA/LAMA). Cumulative distribution function of absolute changes in SGRQ total score at week 56 will be plotted in a figure.

The proportion of subjects with \geq 1 COPD exacerbation during the 56 weeks of treatment will be addressed as a supportive variable to the primary objective. The proportion in each of the three benralizumab dose groups will be compared with the proportion in the placebo group using a logistic regression model with eosinophil cohort (220-299/ μ L or \geq 300/ μ L), country, background therapy (ICS/LABA, LABA/LAMA, or ICS/LABA/LAMA), and number of exacerbations in the year before the study as covariates.

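### The FEV1 and SGRQ repeated-measures model forces one baseline slope on all visits; a baseline-by-visit term would protect Week 56 precision at very small cost

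*Protocol*

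**What the plan says.** Section 8.5.2.1 does not leave the FEV1 model to the SAP. The covariate list includes "visit, the interaction between visit and treatment and baseline pre-bronchodilator" FEV1, and the printed equation ends "ICS/LABA, LABA/LAMA, or ICS/LABA/LAMA) + visit + treatment*visit". Baseline FEV1 enters once, as a main effect. Visit is categorical and "the variance-covariance matrix will be assumed to be unstructured", with compound symmetry as the fallback if the fit does not converge. SGRQ total and domain scores "will be analyzed separately using a similar model as the above model", and E-RS is handled the same way further on in the section.

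FEV1 and SGRQ total score, both at Week 56, are the two key secondary endpoints. Section 8.5 puts them in the confirmatory hierarchy: "Test the two key secondary endpoints for both doses as one family at the FWER of 0.05", by Holm, if both doses succeed on the primary endpoint. The analysed population is the cohort at or above 220/µL (section 8.2: "This addition results in 368 subjects/arm in the" cohort).

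**The concern.** The model lets the visit means, the treatment effects and the covariance vary freely over time, but holds the association with baseline fixed. The confirmatory contrast is at the last visit. If baseline predicts later values less well than earlier ones, the right slope for change at Week 56 is steeper than at Week 4. A single generalised-least-squares slope settles nearer the early visits, where residual variance is smaller. Week 56 is then under-adjusted and its contrast carries residual variance that visit-specific slopes would remove. At stake is a little power for the two key secondary endpoints and, in one dropout pattern, a small shift in the contrast.

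**Working it through.** **The plan's own figure.** The protocol sizes only the primary endpoint: section 8.2 gives "348 subjects with baseline blood eosinophil counts" in the primary cohort per arm for 90% power. A negative binomial Wald calculation (rate 1.0 against 0.7 per 56 weeks, dispersion 0.4, two-sided 4%, both doses significant, shared placebo) gives 91.1% with full follow-up, and 89.8% if the 10% who drop out contribute half their follow-up. The futility loss was not modelled. That figure is consistent, and this point does not depend on it. For FEV1 and SGRQ the protocol gives no SD, correlation, effect size or power, so what follows uses assumed correlations.

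**Inputs from the protocol.** Section 4.2.1 has "scheduled clinic visits at 4-week intervals up to Visit 7 and then at 8 week intervals up to Visit 19". That gives eight post-baseline visits (weeks 4, 8, 16, 24, 32, 40, 48, 56) and 8 − 1 = 7 extra slopes. There are 368 subjects per arm, 4 × 368 = 1,472 in all.

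**Assumptions.** Unit variance at every visit. The correlation depends on the time between two measurements, falling from a short-interval limit r₀ to r₅₆ at 56 weeks, either exponentially or linearly.

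**Formulas.**
- Slope of change on baseline at visit t: βₜ = rₜ − 1.
- Residual covariance of visits s and t: S(s,t) = r(|s−t|) − rₛrₜ, so at Week 56 S₅₆ = 1 − r₅₆².
- Large-sample common slope: b = (1ᵀS⁻¹β)/(1ᵀS⁻¹1).
- Excess Week 56 variance: v = (β₅₆ − b)²/S₅₆.
- Standard-error excess: √(1+v) − 1. Subjects lost per arm: 368 × [1 − 1/(1+v)].

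**Two cases in full.**
- 0.92 to 0.85, exponential: β₅₆ = −0.150, b = −0.100, S₅₆ = 1 − 0.7225 = 0.2775. Then v = 0.050²/0.2775 = 0.9%.
- 0.90 to 0.70, linear: β₅₆ = −0.300, b ≈ −0.146, S₅₆ = 1 − 0.49 = 0.51. Then v ≈ 0.154²/0.51 ≈ 4.6%.

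| Assumed correlation, r₀ to r₅₆ | Variance excess (exponential / linear) | SE excess | Subjects per arm |
|---|---|---|---|
| 0.85 flat | 0 / 0 | 0 | 0 |
| 0.92 to 0.85 | 0.9% / 0.9% | 0.5% | 3 |
| 0.90 to 0.80 | 1.4% / 1.5% | 0.7% | 5 |
| 0.85 to 0.70 | 2.1% / 2.2% | 1.0-1.1% | 8 |
| 0.80 to 0.60 | 2.7% / 2.9% | 1.4-1.5% | 10 |
| 0.90 to 0.70 | 4.4% / 4.6% | 2.2-2.3% | 15-16 |

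A deliberately extreme fall, 0.85 to 0.50 (exponential), gives 7.9% in variance, 3.9% in SE and 27 subjects per arm.

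**In power terms.** A two-sided 5% test with 90% power under visit-specific slopes has Φ[(1.960 + 1.282)/√(1+v) − 1.960]. That is 89.7% for 0.92 to 0.85, 89.4% for 0.85 to 0.70 and 88.7% for 0.90 to 0.70 (linear).

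**Simulation check.** With 4 × 368 subjects, eight visits, 10% completely random monotone dropout, unstructured covariance and 300 runs per case, the mean ratio of model standard errors (common slope over visit-specific) was 1.000 (flat 0.85), 1.005 (0.92 to 0.85), 1.007 (0.90 to 0.80), 1.011 (0.85 to 0.70) and 1.040 (0.85 to 0.50). The flat case shows no measurable penalty for the extra term. Under the compound-symmetric fallback the large-sample loss is about half or less, for example 0.42% against 0.90% in variance for 0.92 to 0.85.

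**Dropout that depends on baseline.** With the same dependence in both arms, the two models' Week 56 contrasts differed by no more than about 0.001 SD. With dependence in one arm only, the common-slope contrast moved by 0.005-0.010 SD (about 10% dropout, 368 per arm) or 0.006-0.016 SD (about 15% missing). With opposite dependence in the two arms it moved by 0.012-0.032 SD. The Week 56 standard error is roughly 0.04-0.06 SD.

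**The case against.** The strongest reply is that nothing here is wrong. A common-slope model with saturated treatment-by-visit means and unstructured covariance is coherent and pre-specified. The protocol contains no evidence that the association with baseline weakens, and if it does not, the loss is exactly zero. In the milder cases 90% power becomes 89.4-89.7%. All of that stands, and it is why the point is minor and conditional.

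A reader might go further and infer that the Week 56 contrast is biased, or that baseline-dependent dropout alone distorts it. The documents do not support either. Randomisation balances baseline between arms, so a wrong slope costs precision without shifting the contrast when data are complete. The same baseline-dependent dropout in each arm leaves it unmoved as well. Only dropout that depends on baseline differently by arm produces a shift, and that shift is small. Section 8.5 keeps data collected after treatment discontinuation, which limits the missing data. Section 3.6.1 does allow phone-only follow-up without further procedures, so some Week 56 spirometry will be missing.

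A reader might also suppose that the extra term is free for every endpoint. It adds parameters to a model for which non-convergence is already foreseen. E-RS is summarised in 14-day means (section 8.4.3), so 56 weeks could give 28 periods and up to 27 extra slopes.

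**Conclusion.** The point holds as a small, optional gain in efficiency. The printed FEV1 model, carried over to SGRQ, imposes a constraint that the analysis does not need. The loss is zero if the baseline slope is constant. It is about 1-5% of Week 56 variance (0.5-2.3% of the standard error, 3-16 of 368 subjects per arm) for assumed declines from 0.92 to 0.85 through 0.90 to 0.70. These figures rest wholly on assumed correlations, equal variances over time and the eight-visit FEV1 schedule. The SGRQ row of Table 3 appears to list fewer visits, so they carry over to SGRQ only approximately. The validity of the planned test is not in question.

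**What to change.** Add baseline-by-visit to the printed FEV1 equation in section 8.5.2.1, and write out the SGRQ total-score model with the same term. For FEV1 this costs seven parameters against about 1,472 subjects, needs no new data and can be settled before unblinding. The small downside is a slightly larger model alongside an existing convergence fallback. For E-RS, add the term only if the number of 14-day periods actually modelled keeps it practical.

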3.6.1 Procedures for discontinuation of a subject from IP

Subjects who prematurely discontinue treatment should return to the study centre and complete the procedures described for the EOT 12 weeks (± 7 days) after the last dose of IP.

It is highly recommended that all study procedures, including any scheduled visits and ePRO completion, are continued till EOT visit, if possible. The subject will bring the ePRO device to the EOT visit.

At EOT visit the subject will be given two options on how to be followed up:

- The subject should be encouraged to return for all regular clinic and phone call visits until he/she completes a total of 56 weeks in the study. At week 56 all the procedures described for Visit 19 are to be conducted
- If the subject cannot comply or does not wish to comply with the option above, he/she will be offered to be followed up on a monthly basis via phone calls while continuing eDiary completion, until the subject completes 56 weeks in the study. No further procedures will be performed. The subject's decision needs to be documented and the specific section in the ICF addendum needs to be signed.

[figure not shown]
The key elements to be collected are AEs/SAEs, changes in concomitant medications, smoking status and COPD exacerbation information.

The Investigator will be instructed to force data transfer from the ePRO device on the day of EOT visit and then to redispense the device to subject. ePRO alerts will still be in place to notify both the subject and the study center of a potential symptom worsening event (see section 5.1.3.7). The subject will be asked to return the ePRO device to the study centre after the subject completes participation in the study (week 56).

- If the subject refuses the two previous options, he/she will need to sign the specific withdrawal of consent portion of the ICF addendum and return all study materials to the study centre.

AstraZeneca will continue to provide maintenance and rescue medications up to 56 weeks from the time of randomisation (see section 3.5.1) unless the patient withdraws consent. It is the Investigator's responsibility to fully evaluate the patient upon discontinuation or withdrawal to ensure that the patient receives appropriate treatment according to his/her clinical status/ condition.

Figure 2 Premature IP discontinuation

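### Minor: the FEV1 repeated-measures fallback goes in one step from unstructured to compound symmetry, which with model-based errors can misstate the Week 56 standard error in either direction

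*Protocol*

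**What the plan says.** Protocol section 8.5.2.1 analyses change from baseline in pre-bronchodilator FEV1 with a repeated-measures model that includes visit as a category and treatment by visit. For the covariance, "the variance-covariance matrix will be assumed to be unstructured". The rule for a failed fit follows at once: "If the procedure does not converge then a compound symmetric variance-covariance matrix will be used instead". No structure is named in between, and no standard-error estimator is named for either fit.

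SGRQ total and domain scores "at Week 56 will be analyzed separately using a similar model as the above model for change from baseline" in FEV1. The fallback probably carries over, but the section does not say so.

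Both endpoints are under alpha control. When both doses succeed on the primary endpoint, section 8.5 says: "Test the two key secondary endpoints for both doses as one family at the FWER of 0.05 using a Holm Procedure". It concludes without qualification: "The overall FWER of the gatekeeping procedure is strongly controlled at 0.05".

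**The concern.** The tested quantity is the treatment difference at Week 56, the last visit. An unstructured matrix estimates that visit's variance separately. Compound symmetry replaces it with one value pooled over all visits. If FEV1 changes become more variable over 56 weeks, a model-based error is too small and the test rejects too often. If they become less variable, the test is conservative.

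The strong-control statement in section 8.5 would then rest, whenever the fallback is used with model-based errors, on equal variance across visits. The protocol neither states nor supports that assumption. Because the protocol fixes the fallback itself, this is a stated choice and not a detail left to the statistical analysis plan. The primary endpoint uses a negative binomial model and is not involved.

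**Working it through.** The protocol gives no SD, correlation, standard error or power for FEV1 or SGRQ, so there is no figure of its own to reproduce.

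**Inputs from the protocol**
- Visits (section 4.2.1): "Subjects will have scheduled clinic visits at 4-week intervals up to Visit 7 and then at 8 week intervals up to Visit 19". Post-baseline this gives Weeks 4, 8, 16, 24, 32, 40, 48 and 56, so 8 visits and 8 × 9 / 2 = 36 unstructured parameters.
- Subjects (section 8.2): 368 per arm in the ≥220/µL population, 1,472 in all.
- Dropout (section 8.2): 10%, assumed there for exacerbations. FEV1 may be missing more often at Week 56, because subjects who stop treatment may choose phone follow-up "until the subject completes 56 weeks in the study. No further procedures will be performed". So 20% is shown as well; that figure is an assumption.

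**Further assumptions**
- Variance is linear in time, from 1 at Week 4 to R at Week 56.
- Six correlation patterns: constant 0.6; 0.4 + 0.6ρ^(lag/4 weeks) with ρ = 0.95 or 0.80; ρ^(lag/4 weeks) with ρ = 0.95, 0.90 or 0.80.
- Dropout is monotone, completely at random, and linear in time.

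**Step 1: complete data, by hand.** The fitted variance is the average over visits. The mean of (week − 4)/52 over the eight visits is (0 + 4 + 12 + 20 + 28 + 36 + 44 + 52)/(8 × 52) = 196/416 = 0.471. Hence

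model-based SE / true SE = √[(1 + 0.471(R − 1))/R], and type I error = 2[1 − Φ(1.96 × SE ratio)].

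- R = 0.8: √(0.906/0.8) = 1.064, type I error 3.7%
- R = 1.25: √(1.118/1.25) = 0.946, 6.4%
- R = 2.0: √(1.471/2) = 0.858, 9.3%

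**Step 2: with dropout.** The large-sample limit of the compound-symmetry likelihood fit replaces the simple average. Ranges are over the six correlation patterns.

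| R | SE ratio, 10% dropout | Type I error, 10% | SE ratio, 20% dropout | Type I error, 20% |
|---|---|---|---|---|
| 0.8 | 1.04–1.07 | 3.7–4.1% | 1.02–1.07 | 3.6–4.6% |
| 1.0 | 0.98–1.00 | 5.0–5.5% | 0.96–1.00 | 5.0–6.0% |
| 1.25 | 0.93–0.94 | 6.4–6.9% | 0.91–0.94 | 6.5–7.5% |
| 1.5 | 0.89–0.90 | 7.6–8.1% | 0.87–0.90 | 7.8–8.8% |
| 2.0 | 0.84–0.85 | 9.5–9.9% | 0.82–0.85 | 9.7–10.7% |

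**Step 3: separate check.** A complete-data simulation of 4,000 trials used assumed SDs in litres. It gave 10.6% for SD rising from 0.20 to 0.30, 1.1% for SD falling from 0.30 to 0.20, and 5.4% for constant SD. Both directions are real.

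**Step 4: family-wise rate in Step 2 of the gatekeeping.** With all four key secondary nulls true and Step 2 open, this is the chance that any of four p-values falls below 0.05/4 = 0.0125. The correlation between doses is 0.5 (shared placebo) and between endpoints 0, 0.3 or 0.5, with 10% dropout. Correct errors give 4.4–4.7%. The fallback on FEV1 alone gives 3.6–4.1%, 4.4–5.0%, 5.4–6.1%, 6.4–7.1% and 7.9–8.8% for the five values of R. If SGRQ were hit with the same SE ratios, the rate would be 6.4–7.5% at R = 1.25 and 11.1–12.7% at R = 2.0.

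**Step 5: alternatives.** Heterogeneous Toeplitz with model-based errors gives a per-test error of 4.2–5.0% at 10%, 20% and 30% dropout. A check under missing-at-random dropout let dropout depend on the last value in one arm only (log-odds rising by 1 per SD of worse value). The largest Week 56 bias relative to unstructured, in standard errors for 368 per arm at 10% and 20% dropout, was:
- Toeplitz: 0.05 and 0.11
- compound symmetry: 0.26 and 0.49
- heterogeneous AR(1): 0.52 and 0.99

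**The case against.** The harm needs three things together: a failed unstructured fit, model-based errors, and variance that changes over time. The first is unlikely and the protocol settles neither of the others. All 30 simulated unstructured fits converged. Even taking the one-sided 95% upper limit on failure, 1 − 0.05^(1/30) = 9.5%, and the worst FEV1-only case, the average family-wise rate is 0.905 × 4.7% + 0.095 × 8.8% = 5.1%. The analysis plan may name a robust estimator or further structures. SGRQ appears to be measured at only about five post-baseline visits (the table layout is broken), so about 15 parameters, and failure there is less likely still. Section 3.6.1 also encourages subjects who stop treatment to keep attending clinic visits, so 20% missing is not established. The remedy is not perfect either: compound symmetry with correct errors still reached 5.7% and 7.8% in the missing-at-random check at 10% and 20% dropout.

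Most of this stands, and it is why the point is minor. Thirty simulated fits are few and say little about the real data, with 24 countries planned and country in the model. The SGRQ figures borrow the FEV1 visit schedule and are illustrative only. What the objection does not remove is that, once the fallback is used, the averaged risk no longer describes the result in hand: the rule as written then gives an error that is right only if the Week 56 variance is near the visit average.

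**Conclusion.** The point holds as a minor, conditional one. The protocol fixes a one-step fallback to a structure that can misstate the Week 56 standard error in either direction if model-based errors are used. Under the assumed variance ratios of 0.8 to 2.0 and 10% dropout, per-test type I error runs from 3.7% to 9.9%. The family-wise rate in Step 2 runs from 3.6% to 8.8% when only FEV1 is affected. Neither the direction nor the size for this trial can be read from the protocol. Extension to SGRQ is an inference. The trigger is unlikely and the primary analysis is untouched.

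**What to change.** Replace the fallback sentence in section 8.5.2.1 with:

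> If the unstructured model does not converge, a heterogeneous Toeplitz matrix will be used; if that also does not converge, compound symmetry with empirical (sandwich) standard errors will be used.

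State whether the same rule applies to SGRQ. Empirical errors at the Toeplitz step are optional. Heterogeneous AR(1) is left out because it was the most biased structure in the missing-at-random check. Compound symmetry comes last because sandwich errors correct the standard error but not that bias.

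The cost is one sentence and a few lines of code. The loss in standard error against unstructured is at most 0.03% for Toeplitz at 10–30% dropout. For compound symmetry with sandwich errors it is up to 1.4% at 10% dropout, 2.9% at 20% and 4.7% at 30%. If variance rises, sandwich intervals are wider than model-based compound-symmetry ones: by 6–8% at R = 1.25 and 17–19% at R = 2.0 with 10% dropout. That width is needed for correct coverage.
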